8.8.4. Clinical Safety Laboratory Assessments

- A central laboratory will be used in this study.
- Refer to [Appendix 2](#) for the list of clinical laboratory tests to be performed and to the SoA (Section 1.3) for the timing and frequency.
- The investigator must review the laboratory report, document this review, and record any clinically relevant changes occurring during the study in the AE section of the CRF. The laboratory reports must be filed with the source documents. Clinically significant abnormal laboratory findings are those which are not associated with the underlying disease, unless judged by the investigator to be more severe than expected for the participant's condition.
- All laboratory tests with values considered clinically significantly abnormal during participation in the study or within 60 days after the last dose of study intervention should be repeated until the values return to normal or baseline or are no longer considered significantly abnormal by the investigator or medical monitor.
- If such values do not return to normal/baseline within a period of time judged reasonable by the investigator, the etiology should be identified and the sponsor notified.
- All protocol-required laboratory assessments, as defined in [Appendix 2](#), must be conducted in accordance with the laboratory manual and the SoA.
- Laboratory toxicity will be graded using the Adverse Event and Laboratory Value Severity Grading Table ([Appendix 2](#), Section 10.2.1). The Table is based upon publicly available Tables from the National Institute of Allergy and Infectious Disease Division of Microbiology and Infectious Diseases

(www.niaid.nih.gov) and Common Terminology Criteria for Adverse Events (CTCAE) Version 4.0 ([U.S. Department of Health and Human Services](#), 2010).

- Note: If a laboratory value is reported that requires withholding of further dosing, the site personnel must contact the parent/caregiver promptly to ensure no further injections are administered until reviewed with the investigator if the next administration would be away from the clinic.

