10.2. Appendix 2: Clinical Laboratory Tests

- The tests detailed in [Table 2](#) will be performed by the central laboratory.
- Protocol-specific requirements for inclusion or exclusion of participants are detailed in Section [5](#) of the protocol.
- Additional tests may be performed at any time during the study as determined necessary by the investigator or required by local regulations.
- Pregnancy testing
 - Refer to Section [5.1](#) Inclusion Criteria for screening pregnancy criteria.
 - Pregnancy testing (urine or serum as required by local regulations) should be conducted at monthly intervals during intervention
 - Pregnancy testing (urine or serum as required by local regulations) should be conducted at the end of relevant systemic exposure.
 - Additional serum or urine pregnancy tests may be performed, as determined necessary by the investigator or required by local regulation, to establish the absence of pregnancy at any time during the participant's participation in the study.

Table 2 **Protocol-Required Safety Laboratory Assessments**

Laboratory Assessments	Parameters			
Hematology	Platelet Count	RBC Indices: MCV MCH %Reticulocytes	WBC count with Differential: Neutrophils Lymphocytes Monocytes Eosinophils Basophils	
	RBC Count			
	Hemoglobin			
	Hematocrit			
Clinical Chemistry ¹	Calcium	Potassium	Aspartate Aminotransferase (AST)/ Serum Glutamic-Oxaloacetic Transaminase (SGOT)	Total bilirubin
	Calcium corrected for Albumin Inorganic Phosphate	Sodium	Alanine Aminotransferase (ALT)/ Serum Glutamic-Pyruvic Transaminase (SGPT)	Total Protein

Laboratory Assessments	Parameters			
	Carbon dioxide	Magnesium	Alkaline phosphatase	Albumin
	Glucose (nonfasting)		Gamma glutamyl transpeptidase (GGT)	Creatinine
	Uric acid	Blood urea nitrogen (BUN)	BUN/creatinine ratio	Estimated Creatinine Clearance/GFR (Schwartz ²)
Routine Urinalysis	
 pH, glucose, protein, blood, ketones, occult blood by dipstick Microscopic examination (if blood or protein is abnormal) 			
Biological markers	
 BLyS protein Serum complement (C3 and C4) C-Reactive Protein (CRP) Peripheral lymphocytes including B lymphocytes (CD20+, CD20+/27+ memory, CD20+/27– naïve, CD19+/27br/38br 'SLE subset'). 			
Immunoglobulins	
 Serum immunoglobulin isotypes: IgG, IgM, IgA 			
PK	
 Blood collection 			

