7.2. Other Efficacy Analyses

7.2.1. Proteinuria

Proteinuria shifts from baseline will be summarized by visit [T2.04].

Baseline proteinuria data will be summarized as the number and percentage of subjects who are normal (≤0.5 mg/mg) or high (>0.5 mg/mg). For each post-baseline visit the data will be summarized by normal or high baseline status. Among subjects normal at baseline, the shifts presented will be 'No Change' or 'Normal to High'. Among subjects high at baseline, the shifts presented will be 'No Change' or 'High to Normal'.

As well as presenting the data for each visit, the proteinuria shifts will be summarized based on shifts at any time post-baseline. Among subjects with normal proteinuria at baseline, the number and percentage of subjects with at least one high post-baseline value will be presented as 'Normal to High'; subjects who never experience a high proteinuria value post-baseline will be presented as 'No Change'. Among subjects with high baseline proteinuria, subjects with at least one normal post-baseline value will be presented as 'High to Normal'; subjects who never experience a normal post-baseline value will be presented as 'No Change'.

No statistical tests will be performed.

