8.2. Clinical Laboratory Analyses

Laboratory evaluations including the analyses of Chemistry laboratory tests, Hematology laboratory tests, Urinalysis and liver function tests will be based on GSK Core Data Standards.

For laboratory analyses, analytes will be summarized and analyses will be performed based on the observed data, no imputation will be done for missing data. Baseline is defined as described in Section 5.4.

Laboratory toxicity will be graded using the Adverse Event and Laboratory Value Severity Grading Table (see Protocol Appendix 2, Section 10.2.1). The Table is based upon publicly available Tables from the National Institute of Allergy and Infectious Disease Division of Microbiology and Infectious Diseases (www.niaid.nih.gov) and Common Terminology Criteria for Adverse Events (CTCAE) Version 4.0 (U.S. Department of Health and Human Services, 2010). Toxicity grades provided by the laboratory will be used. Any laboratory parameters where toxicity grades are expected but not provided by the laboratory will be programmed according to the Protocol.

If a numeric laboratory value, has a non-detectable level reported in the database, then typically the numeric value is missing, and a character value starting with '<x' or '>x' is present. A numeric value will be derived using the number of decimal places in the observed character values i.e.

- 2 Decimal Places = '<x' becomes x-0.01
- 1 Decimal Place = '>x' becomes x+0.1
- 0 Decimal places = '<x' becomes x-1

Laboratory parameters are shown in Table 5, split by output category (hematology, liver function, electrolytes, other chemistries, urinalysis and immunoglobulins) and indicating which type of outputs are applicable for each parameter.

Table 5 Laboratory Parameters

Laboratory Parameter	Lab Results by Visit (Section 8.2.1)	Toxicity Grade (Section 8.2.2 and Section 8.2.3)	Reference Range Shifts (Section 8.2.4)
Hematology		 	
Basophils (10^9/L)	Yes		Yes
Basophils/Leukocytes (%)	Yes		Yes
Eosinophils (10^9/L)	Yes		Yes
Eosinophils/Leukocytes (%)	Yes		Yes
Ery. Mean Corpuscular Hemoglobin (pg)	Yes		Yes
Ery. Mean Corpuscular Volume (fL)	Yes		Yes
Erythrocytes (10^12/L)	Yes		Yes
Hematocrit (%)	Yes		Yes
Hemoglobin (g/L)	Yes	Yes	
Leukocytes (10^9/L)	Yes	Yes	
Lymphocytes (10^9/L)	Yes	Yes	
Lymphocytes/Leukocytes (%)	Yes		Yes
Monocytes (10^9/L)	Yes		Yes
Monocytes/Leukocytes (%)	Yes		Yes
Neutrophils (10^9/L)	Yes	Yes	
Neutrophils, Segmented (10^9/L)	Yes		Yes

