8.2.1. Laboratory Assessments by Visit

Descriptive summary statistics for each laboratory parameter will be displayed for each visit, for hematology [T3.18], liver function [T3.19], electrolytes [T3.20] and other chemistries [T3.21]. No statistical tests will be performed.

A line graph will be produced for each lab parameter which displays the mean value (±SE) by visit for hematology [F3.01], liver function [F3.02], electrolytes [F3.03] and other chemistries [F3.04].

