8.2.4. Laboratory Reference Range Shifts from Baseline by Visit

For laboratory tests without toxicity grades, shifts relative to the normal range will be summarized for each lab parameter within hematology [T3.34], liver function [T3.35], electrolytes [T3.36], other chemistries [T3.37] and urinalysis [T3.38]. No statistical tests will be performed.

For the 'shift to low' category, the percentage of subjects with at least one low post-baseline value will be displayed using the categories: 'remained low' and 'shift normal/high to low'.

For the 'shift to normal/high' category, the percentage of subjects with at least one normal/high post-baseline value will be displayed using the categories: 'remained normal/high' and 'shift low to normal/high'.

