13.4. Appendix 4: Derived and Transformed Data

13.4.1. General

Multiple Measurements at One Analysis Time Point

- For continuous data, if there are two values within a time window (as per Section 13.1.1) the value closest to the target day for that window will be used. If values are the same distance from the target, then the mean will be taken. All data will be presented in the listings.
- For categorical data, if there are two values within a time window (as per Section 13.1.1) the value closest to the target day for that window will be used. If values are the same distance from the target, then the value prior to the target day will be taken. All data will be presented in the listings.
- Participants having both High and Low values for Normal Ranges at any post-baseline visit for safety parameters will be counted in both the High and Low categories of "Any visit post-baseline" row of related summary tables.

Study Day

- Calculated as the number of days from First Dose Date:
 - Ref Date = Missing → Study Day = Missing
 - Ref Date < First Dose Date → Study Day = Ref Date First Dose Date
 - Ref Date ≥ First Dose Date → Study Day = Ref Date First Dose Date + 1

Study Completion

- A participant is considered to have completed the primary study if he/she has completed all phases during Parts A and B of the study, including the Week 52 Visit, as defined in the Schedule of Activities (SoA) Section 1.3 of the protocol.
- A participant is considered to have completed Part A of the study if he/she has completed all 12
 weeks of the treatment phase, including the Week 12 Visit, as defined in the SoA (see Section 1.3 of
 the protocol).
- Participants who withdraw from study treatment prior to the end of Part A and participants who
 complete Part A but do not wish to continue into Part B are required to complete 8 and 16 week
 follow-up visits.
- Participants who withdraw from treatment prior to Week 12, should complete an early withdrawal (EW) visit, in addition to the 8 and 16 week follow-up visit and assessments. The EW visit requires identical assessments and procedures to the Week 12 (Day 85/81) visit.
- Participants who withdraw from treatment prior to Week 52, should complete an EW visit, in addition to the 8 and 16 week follow-up visit and assessments. The EW visit requires identical assessments and procedures to the Week 52 visit.

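### SAP 8.2.4 pools normal with high, so as written shift tables T3.34 to T3.38 cannot count participants newly above the upper limit for the 24 ungraded laboratory parameters

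*SAP*

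**What the plan says.** For laboratory tests without toxicity grades, SAP 8.2.4 says that "shifts relative to the normal range will be summarized for each lab parameter" in hematology, liver function, electrolytes, other chemistries and urinalysis (T3.34 to T3.38). It then defines two blocks:

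- A 'shift to low' block for subjects with at least one low post-baseline value, split into 'remained low' and 'shift normal/high to low'.
- A 'shift to normal/high' block, for which "the percentage of subjects with at least one normal/high post-baseline value will be displayed using the categories" 'remained normal/high' and 'shift low to normal/high'.

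SAP Table 5 marks which parameters go into these tables.

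SAP 13.4.1 adds a general handling rule. Participants who have both High and Low values for a safety parameter after baseline "will be counted in both the High and Low categories" of a row covering any post-baseline visit. It does not say which tables it means.

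**The concern.** A reference-range shift table is normally read in both directions: who fell below range, and who rose above it. Here the second question has no row, and a participant whose value rises above the upper limit is tabulated as unchanged.

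The protocol treats high as a direction of interest for at least two of the tests:

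- **Eosinophils.** Protocol Appendix 5 (10.5) gives eosinophilia as an example of a hypersensitivity symptom and asks for a differential count to look for it after a liver event. Hypersensitivity reactions are adverse events of special interest (Protocol 8.9.3, SAP 8.1.5). Eosinophils have no toxicity grade.
- **Urine leukocytes.** Protocol Appendix 10 scores pyuria in SELENA SLEDAI. Urine leukocytes have neither a toxicity grade nor a by-visit table.

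At stake is whether the clinical study report can state how many participants moved above range on these tests.

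**Working it through.** The documents state no figure to reproduce. The check has three parts: a count, a mapping and a search for other outputs.

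**1. How many parameters.** SAP Table 5 rows marked for reference-range shifts:

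| Category | Parameters | n |
|---|---|---|
| Hematology | basophils (2), eosinophils (2), MCH, MCV, erythrocytes, hematocrit, lymphocyte %, monocytes (2), segmented neutrophils (2), neutrophil %, reticulocyte % | 15 |
| Liver function | direct bilirubin | 1 |
| Electrolytes | calcium, carbon dioxide | 2 |
| Other chemistries | GFR, protein, urea, urea nitrogen/creatinine | 4 |
| Urinalysis | leukocytes, pH | 2 |

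15 + 1 + 2 + 4 + 2 = 24. None of the 24 is also marked for a toxicity grade.

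**2. Where each change lands.** With L, N and H for low, normal and high, there are nine baseline-to-post-baseline changes for the four rows in 8.2.4:

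| Row in 8.2.4 | Changes it holds |
|---|---|
| remained low | L→L |
| shift normal/high to low | N→L, H→L |
| remained normal/high | N→N, **N→H**, H→N, H→H |
| shift low to normal/high | L→N, **L→H** |

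Both new-high changes (bold) share a row with changes that are not new highs, so no combination of the four rows recovers their number.

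Illustration, assuming 28 treated participants, all normal at baseline and none ever low. If 0, 5 or 20 of them go above range, the table shows 28 of 28 in 'remained normal/high' each time. A table with a separate high block would show 0, 5 or 20.

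**3. Whether another output counts new highs.**

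- *Toxicity tables (SAP 8.2.2, 8.2.3).* The 24 parameters are not graded. The five graded hematology tests (hemoglobin, leukocytes, lymphocytes, neutrophils, platelets) are graded for low values only in Protocol 10.2.1, so 0 of 5 captures a high. The leukocyte grade therefore says nothing about high eosinophils.
- *By-visit statistics (SAP 8.2.1).* T3.18 to T3.21 cover 24 − 2 = 22 parameters; urine leukocytes and urine pH are not included. The 75th percentile and maximum show that high values exist, but not how many participants crossed the limit from baseline.
- *Listings L3.12 to L3.16 (SAP 8.2).* These give every result without a tabulated shift.
- *Adverse events.* Under Protocol 8.8.4 the investigator must "record any clinically relevant changes occurring during the study in the AE section of the CRF", which depends on judgement.
- *SELENA SLEDAI.* Pyuria is an item, assessed at screening, Day 1, Week 12 (Day 81 in Cohort 2) and Week 52. T1.14 tabulates items at baseline, but SAP Section 7 describes no post-baseline item table.
- *The 13.4.1 rule.* It needs a High category. SAP 8.2.4 has none, 8.2.5 counts only values below the lower limit, and the shift tables in 11.2.4 pool normal with high for immunoglobulins and complement. The rule has nothing to apply to.

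**The case against.** The strongest reply is that the tables may already be right. The SAP sends the reader to mock displays that are not in the documents, and 13.4.1 makes a High row in those shells plausible. That stands: what can be shown is a defect in the text of 8.2.4, not in the tables that will be produced. Either way something needs correcting, the shells or the wording.

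A second reply is low materiality. The study is descriptive, with about 28 participants, and SAP Section 8 places laboratory summaries among the other safety endpoints, apart from the secondary endpoint of AEs, SAEs and AESIs. A reader could count new highs from the listings. This also stands and limits the size of the point. It does not explain why a table meant to show shifts should label a shift as no change.

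Third, pooling normal with high is a convention used elsewhere, in SAP 11.2.4. For immunoglobulins and complement the low contrast is the one of interest; 8.2.4 gives no reason to carry it over to eosinophils or urine leukocytes. SAP 7.2.1 shows that an any-time count of new highs fits the plan: for proteinuria, subjects normal at baseline "with at least one high post-baseline value will be presented as" 'Normal to High'. That is an efficacy table with a fixed cut-off and two states, so it is a precedent and not proof of inconsistency.

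Three stronger readings are tempting but not supported:

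- **That 13.4.1 contradicts 8.2.4.** It is a general rule attached to no named table. Without a High category it is idle, not violated.
- **That high laboratory values go unseen.** The listings, by-visit statistics and AE reporting show otherwise.
- **That all 24 parameters are equally affected.** For GFR, low is the direction of concern, and calcium, urea and direct bilirubin have related graded tests (albumin-corrected calcium, creatinine, total bilirubin). The documents set no rule for which parameters matter, so no reduced count is offered here.

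**Conclusion.** The point holds for the SAP as written. For 24 ungraded parameters across T3.34 to T3.38, participants newly above the upper limit cannot be counted, because normal-to-high and low-to-high changes are pooled with other changes. No other table described in the SAP counts them. Eosinophils and urine leukocytes are the clearest cases.

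The number of participants affected cannot be derived from the documents. For urine leukocytes it may be small: Protocol Table 2 plans urine microscopy only when blood or protein is abnormal, and its dipstick list does not include leukocytes. I assume the result comes from microscopy.

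The conclusion rests on the text of 8.2.4 and on Table 5 being complete. It does not touch the primary or secondary endpoints. It should be corrected before the tables are produced, as a limited repair to descriptive safety tables.

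**What to change.** Keep both existing blocks of SAP 8.2.4 and add a third, for example:

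> For the 'shift to high' category, the tables will show how many subjects (number and percentage) had one or more high values after baseline, split into 'remained high' and 'shift normal/low to high'. Subjects with both High and Low values after baseline are counted in each block, as set out in Section 13.4.1.

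The block should be added and should not replace the 'shift to normal/high' block. That block holds 'shift low to normal/high', the only planned count of participants who come back from a low baseline on these tests. A footnote should say that the blocks overlap, since a high value also counts as normal/high.

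Align the shells for T3.34 to T3.38. If they already carry a High category, correct the text of 8.2.4 to match them. The 13.4.1 rule then has a table to apply to. Leave 11.2.4 unchanged.

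The cost is one SAP paragraph and two more rows per parameter (2 × 24 = 48 rows) in at most five tables, with no new data.

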8.2.5. Immunoglobulin Levels Below LLN by Visit

The number and percentage of subjects with immunoglobulin values (IgG, IgA, and IgM) below the LLN at each visit will be presented for all subjects [T3.39]. No statistical tests will be performed.

8.2.6. Liver Events

A listing will be produced for liver monitoring/stopping events reported [L3.25]. The alcohol intake at onset of the liver event will be presented [L3.26].

8.2.7. Immunogenicity

For the immunogenicity assessment for belimumab, two types of antibody assays will be performed, i.e. a binding assay and neutralizing assay. For the binding assay, there will be 3-testing steps. A screening assessment is performed which produces a result of positive or negative. For samples with a positive screening result, a confirmation assay is then carried out, which also produces a result of positive or negative. For samples with a positive confirmation result, a titer value will also be obtained to quantify the degree of binding in a titration assay step. Subjects will be viewed as positive for the binding assay

if the confirmation assay was positive. Subjects, who tested positive for the binding assay, will be tested for the neutralizing assay, which again produces a result of positive or negative.

For incidence of subjects with positive binding antibody during the study period, a table will be produced summarizing results for the binding antibody assay by visit. The table will include the number and proportion of subjects in each results category for each visit in the study period (including early withdrawal visit). Binding confirmatory assay results will be categorized as negative, persistent positive (defined as a positive immunogenic response for at least two consecutive assessments during the study period or a single result at the final assessment in the study period) or transient positive (defined as a single positive immunogenic response that does not occur at the final assessment in the study period).

Results will be summarized by visit and any time post baseline [T3.40].

A listing of immunogenicity results will be presented for any subject who had a positive result at any time [L3.24].

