In Clinic Administration of Belimumab (Cohort 3 <30 kg) ⁷		X		X	X	X	X ⁹	
PK Sampling ⁸			X	X	X	X	X	X

1. 8- and 16-week follow-up is required for participants who withdraw from study treatment prior to the end of Part A and for participants who complete Part A but do not wish to continue into Part B. For participants who withdraw from treatment prior to Week 12, in addition to the 8- and 16-week follow-up visit and assessments, an early withdrawal visit (EW) should be completed. The EW visit requires identical assessments and procedures to the Week 12 visit.
2. 16-week follow-up requires a phone call to collect AEs, concomitant medications and the results of home urine pregnancy test (if applicable) for female participants. NOTE: the 16-week follow-up may be performed at a clinic visit per local requirement.
3. Full Physical Examination is required at screening (Section 8.1). An abbreviated/symptom-driven exam can be done thereafter.
4. Please refer to Section 8.9.1. for the time period for collection of AEs/SAEs
5. Serum pregnancy test required at screening for all females of childbearing potential. Urine pregnancy test is sufficient for all subsequent visits. A home pregnancy test (urine) will be provided to participants for the 16-week follow-up pregnancy assessment.
6. Cohort 1 (≥ 50 kg at baseline): Study drug to be administered weekly in Part A. Administration in clinic is mandated where specified in the Schedule of Activities (SOA), otherwise at home self-administration is encouraged (see Section 6.4). For the first 2 doses (Day 1 and Week 0) participants must be observed for 3h post belimumab injection (see Section 6.4).
7. Cohort 3 (< 30 kg at baseline): Study drug to be administered every 2 weeks in Part A. Administration in clinic is mandated where specified in the SOA, otherwise at home self-administration is encouraged (see Section 6.4). For the first 2 doses (Day 1 and Week 1), participants must be observed for 3h post belimumab injection (see Section 6.4).
8. Samples must be taken pre-dose.
9. Dosing only occurs for participants who elect to continue in Part B.
10. Participants in Cohort 3 (< 30 kg) will have the screening blood collection and testing split across 2 visits separated by at least 2 weeks and between the 2nd screening and Day 1 visits to ensure the blood volume collected remains within local guidelines. Note: This may also apply to participants ≥ 30 kg according to local guidelines.

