1. If participants withdraw from treatment prior to Week 52, in addition to the 8- and 16-week follow-up visit and assessments, an early withdrawal (EW) visit should, if possible, be completed. The EW visit requires identical assessments and procedures to the Week 52 visit. The 8- and 16-week follow-up visits are **NOT** required for participants who are eligible for and are enrolled into the optional access extension phase.
2. 16-week follow-up requires a phone call to collect AEs, concomitant medications and report results of home urine pregnancy test (if applicable) for female participants. NOTE – the 16-week follow-up may be performed at a clinic visit per local requirement.
3. An abbreviated/symptom-driven exam can be done as described in Section 8.8.1
4. Please refer to Section 8.9.1 for the time period for collection of AEs/SAEs.
5. Urine pregnancy test is sufficient for all visits in Part B. A home pregnancy test (urine) will be provided to participants for the 16-week follow-up pregnancy assessment.
6. Cohort 1 (\geq 50 kg at baseline): Study drug to be administered weekly. Wherever the dosing days coincide with clinic visits IP administration in clinic is mandated. PK and/or biomarker sample collection, where specified, must be pre-dose at these visits.
7. Cohort 2 (\geq 30 kg - <50 kg at baseline): Study drug to be administered every 10 days. Wherever the dosing days coincide with clinic visits IP administration in clinic is mandated. PK and/or biomarker sample collection, where specified, must be pre-dose at these visits.
8. Cohort 3 (15 - <30 kg at baseline): Study drug to be administered every 2 weeks. Wherever the dosing days coincide with clinic visits IP administration in clinic is mandated. PK and/or sample collection, where specified, must be pre-dose at these visits.

9. In Part B the dosing frequency may be switched according to any change in body weight. Please refer to Section [6.6](#) Dose Modification. IF a participant switches dosing frequency due to weight changes during Part B, the last IP administration will be according to the schedule provided at Week44. Individual cases will be consulted with and resolved by the Medical Monitor.
10. Samples must be taken pre-dose where the dose is administered on a clinic visit day.

1.3.4. SOA 4 Optional Access Extension Phase - Applies exclusively to eligible participants who complete Part B

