Administration of belimumab may result in infusion or injection-related systemic reactions and allergic/hypersensitivity reactions.	
Administration of belimumab may result in infusion and hypersensitivity reactions, which can be severe and can be fatal. Delay in the onset of serious hypersensitivity reactions can occur. Belimumab has been associated with delayed type non-acute hypersensitivity reaction (HSR)/serum sickness, although no relationship to anti-drug antibody (ADA) has been established.
 
Infusion or injection-related systemic reactions and hypersensitivity reactions occur more frequently with the first two doses and tend to decrease with subsequent doses. In studies involving subcutaneous administration, injection site reactions occurred more frequently following subcutaneous administration than with intravenous infusion. The most frequent
	
Participants with a history of an anaphylactic reaction to parenteral administration of contrast agents, human or murine proteins, or monoclonal antibodies or to any of the excipients of the study drug will be excluded from this study.
 
Participants will remain under clinical supervision for 3 hours after completion of the first 2 belimumab injections in Part A.
 
The presence of ADAs will be monitored with collection at baseline, Weeks 4, 12, 24, 52, and 8-week post-treatment follow-up.
 
Participants will be made aware of the potential risk, the signs and symptoms of such reactions, and the importance of immediately seeking medical attention. Patients will be given an alert card for hypersensitivity/allergic reactions.

Potential Risk of Clinical Significance	Summary of Data/Rationale for Risk	Mitigation Strategy
	injection site-related event was pain at the site of injection.	
Malignancy		
As with other immunomodulating agents, the mechanism of action of belimumab may increase the potential risk for the development of malignancies.	Immunomodulatory drugs like belimumab may increase the risk of malignancy. To date, no causal relationship between belimumab and malignancy, including B cell lymphoma, has been detected.	Participants with a history of malignancy in the 5 years prior to screening will be excluded. Monitor patients for signs and symptoms of malignancy, monitor laboratory values, request that patients report signs and symptoms. Treat appropriately.
Interactions with Vaccinations		

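### The SAP's persistent and transient ADA classes leave some positive children unclassified, and no class uses the Day 1 result

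*SAP*

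**What the plan says.** SAP Section 8.2.7 treats a child as positive for binding antibody when the confirmation assay is positive, and a titer is then measured. The classification begins: "Binding confirmatory assay results will be categorized as negative, persistent positive". Persistent is defined as "a positive immunogenic response for at least two consecutive assessments during the study period or a single result at the final assessment" of the study period. Transient is "defined as a single positive immunogenic response that does not occur at the final assessment". Table T3.40 gives the count and proportion of children in each category: "Results will be summarized by visit and any time post baseline". Listing L3.24 shows the results of every child who was ever positive.

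On sampling, Protocol Section 2.3.1 states: "The presence of ADAs will be monitored with collection at baseline, Weeks 4, 12, 24, 52, and 8-week post-treatment follow-up". Two groups have fewer samples:

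- **Access-extension entrants.** The Part B schedule (Protocol Section 1.3.3, note 1) says that the 8- and 16-week follow-up visits are not "required for participants who are eligible for and are enrolled into the optional access extension phase".
- **Children who do not enter Part B.** They have Weeks 4 and 12 and then a follow-up sample (Protocol Sections 1.3.1 and 1.3.2, note 1): "8- and 16-week follow-up is required for participants who withdraw from study treatment prior to the end of Part A". The same note covers those who complete Part A and stop there.

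SAP Section 5.4 makes the Day 1 pre-dose sample the immunogenicity baseline. Exclusion criterion 13 (Protocol Section 5.2) bars earlier belimumab. Section 8.2.7 does not define its study period. The nearest definition, on study in SAP Section 5.2, starts on Day 1.

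**The concern.** There are two separate problems.

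**The classes are not exhaustive.** Take a child positive at Weeks 4 and 24 and negative at Week 12, Week 52 and follow-up. The child is not negative. There are two positives, so neither is single. They are not consecutive, and the last sample is negative. The SAP gives no place for this child, so the programmer must invent a rule once the data are in, or the categories will not sum to the total.

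**Baseline status is collected but not used.** No child should have had belimumab before, so a positive on Day 1 is pre-existing reactivity. If it continues unchanged, the child is reported in the same row, and possibly the same persistent class, as a child who became positive on drug. Elsewhere the SAP does take the pre-treatment state into account: treatment-emergent adverse events (Section 13.2.2), toxicity-grade worsening (8.2.3) and autoantibody shifts by baseline status (11.2.4). ADA monitoring is also listed in Protocol Section 2.3.1 among the mitigations for hypersensitivity risk, so a reader will want to know which positives arose on treatment.

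**Working it through.** The plan states no ADA rate or other figure that depends on the rule, so there is nothing to reproduce. The check lists every positive/negative pattern over the scheduled samples and applies the definitions child by child.

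**Inputs.** Post-baseline ADA samples, in order:

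- Full follow-up: Weeks 4, 12, 24, 52 and the 8-week follow-up (n = 5).
- Access-extension entrants: Weeks 4, 12, 24, 52 (n = 4).
- Part A only: Weeks 4, 12 and the 8-week follow-up (n = 3).

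Cohort 2's Day 31 and Day 81 samples are presented as Weeks 4 and 12 (SAP Table 4).

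**Step 1: patterns with no class.** With n samples there are 2^n − 1 patterns with at least one positive. A pattern is unclassified if it has two or more positives, no two adjacent, and a negative last sample. Here any positive at the final assessment is taken as persistent, which is the reading more favourable to the SAP.

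- n = 5: 2^5 − 1 = 31. Unclassified: Weeks 4+24, 4+52 and 12+52, so 3 of 31.
- n = 4: 2^4 − 1 = 15. Unclassified: Weeks 4+24, so 1 of 15.
- n = 3: 2^3 − 1 = 7. Unclassified: none, so 0 of 7.

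**Step 2: the stricter reading.** If the final-assessment clause applies only when that sample is the child's sole positive, patterns with a positive last sample, at least one other positive and none adjacent also drop out.

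- n = 5: four more (Week 4, 12 or 24 with follow-up, and Weeks 4+24 with follow-up), so 3 + 4 = 7 of 31.
- n = 4: two more (Weeks 4+52 and 12+52), so 1 + 2 = 3 of 15.
- n = 3: one more (Week 4 with follow-up), so 0 + 1 = 1 of 7.

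**Step 3: what the gap changes.** Positivity rests on the confirmation assay alone, so every unclassified child is still ADA-positive. Overall incidence does not change; only the persistent/transient split does.

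**Step 4: the Day 1 result.** Under full follow-up, 2^5 = 32 patterns have a positive Day 1. Of these, 32 − 1 = 31 have a later positive and enter the post-baseline row. The exception, positive on Day 1 only, does not.

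Whether Day 1 belongs to the study period also matters. A child positive only on Day 1 and Week 4 is persistent if it does and transient if it does not. A child positive only on Day 1 and Week 12 is unclassified if it does and transient if it does not.

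**Step 5: size per child.** Taking the planned enrolment of about 28 as the denominator, 1/28 = 3.6%. With the 24 evaluable at Week 12, 1/24 = 4.2%.

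**The case against.** The strongest reply is that Section 8.2.7 speaks of categorizing results and tabulates them by visit. Read result by result, an isolated positive at Week 4 and another at Week 24 could each be called transient, and nothing would be left over. The wording is loose enough to suggest this. But the same section counts children in each category, persistent is defined across a child's successive samples, and the any-time row needs one class per child. The per-result reading does not fit that table.

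Other replies stand and limit the point:

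- ADA is not among the listed endpoints, all analyses are descriptive, and nothing in the plan depends on the split.
- A by-visit table that includes Day 1 would show the number of baseline positives, and L3.24 lets a reader trace each positive child in a trial of this size. This allows repair by hand but is not a prespecified rule.
- The mock displays were not available, so the layout of T3.40 cannot be checked.

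Three stronger inferences are tempting, and the documents do not support them. First, a reader might infer that the class gap alters ADA incidence; it does not (Step 3). Second, 3 of 31 might be read as about a tenth of positive children. It counts possible patterns, and no ADA rate is given from which to estimate a frequency. Third, one might say that every Day 1 positive inflates a treatment-emergent figure. Only those also positive later enter the post-baseline row, and the SAP does not call that row treatment-emergent.

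**Conclusion.** The point holds and is minor. Applied per child, the three classes leave out non-consecutive positives followed by a negative final assessment: 3 of 31 positive patterns with full follow-up, 1 of 15 for access-extension entrants and 0 of 7 for Part A-only children. This rests on counting any positive at the final assessment as persistent, classifying on post-baseline samples only, and complete sampling. The stricter reading gives 7 of 31, 3 of 15 and 1 of 7.

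Separately, children positive on Day 1 and again later cannot be told apart in the classes from those who turned positive on drug. Each would move the post-baseline proportion by about 3.6 points if the denominator is 28. How many children either problem would affect cannot be estimated from the documents. No sample size, power or error rate is involved.

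**What to change.** Amend SAP Section 8.2.7 as follows:

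1. Classify on post-baseline samples only, and say that the study period for this purpose excludes Day 1.
2. Define persistent as at least two consecutive post-baseline positives, or any positive at the final assessment.
3. Define transient as any other post-baseline positive.
4. Report treatment-emergent ADA (negative on Day 1, positive later) separately from children positive on Day 1, and list the titers already collected for the latter.

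Every positive pattern then has exactly one class. With five samples, 24 are persistent and 4 + 3 = 7 transient, and 24 + 7 = 31. With four samples it is 11 + 4 = 15, and with three 5 + 2 = 7. The documents give no titer-rise threshold, so titers can simply be listed unless the sponsor prespecifies one.

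The cost is a few sentences in the SAP and one extra split of T3.40. No new samples or assays are needed.
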